**Brief Internet Interventions to Support Mental Health Study Protocol**  
**(Includes analysis plans and information sheets)**

**April 6, 2023**

## **Aim 1: Evaluating a Single-session Intervention for Loneliness**

### **Procedure**

#### *Sample recruitment*

Researchers will use social media and the University of California, Irvine Social Ecology subject pool to recruit a diverse online sample of English-speaking participants aged 16+ with access to the internet and a computer, tablet, or smartphone. Researchers will advertise the study on social media using both paid and unpaid posts on several platforms, including Instagram, Reddit, Tumblr, Twitter, Facebook, LinkedIn, 4chan, and others. Researchers may also use the online subject recruitment platform Researchmatch.

Recruitment materials will explain that participants must be at least 16 years old, speak English, and have access to internet and a computer, smartphone, or tablet to be allowed to participate in the study. After a brief introduction to the study, researchers will first ask participants to complete the ULS-3 loneliness measure. To ensure a sufficient number of participants struggling with loneliness for analysis, if one's score on the measure meets the criterion for "struggling with loneliness", they will be invited to participate in the study and be offered a reimbursement of a \$10 Amazon gift card that researchers will email them once they complete the final follow-up 8 weeks later. Individuals will be considered to be struggling with loneliness if their score on the ULS-3 is 6 or higher and they answer affirmatively that their loneliness is causing them distress (Steptoe et al., 2013).

Researchers will only allow participants to complete the study once. If one's score on the loneliness measure does not meet the criterion, researchers will still give them the opportunity to complete the study without compensation. Researchers will also offer them access to the loneliness programs if they prefer to not participate in the study. Researchers will offer those who participate through the UC Irvine subject pool 1 hour of participation credit for completing the first part of the study. If UC Irvine subject pool participants meet criteria for struggling with distress, they will also be offered a \$10 gift card for completing all parts of the study.

#### *Study process*

After participants read the study information and agree to participate, they complete baseline self-report measures of mental health outcomes and demographics. Next, they complete the intervention (see materials for intervention information). After they complete the intervention, participants complete a few brief measures of hope, agency, meaning in life, and engagement with the intervention platform. 4 and 8 weeks later, they receive links via email to complete follow-up measures of mental health outcomes and engagement. After the 8-week follow-up, participants are offered access to all three conditions in PDF and browser forms. The study will be conducted using the secure online survey and "experience management" platform Qualtrics. Researchers will include anti-fraud / anti-bot measures in the survey.

## Materials

Researchers created a 25-minute loneliness SSI and a 3-week loneliness intervention by adapting Käll et al.'s 9-week therapist-supported iCBT for loneliness (Käll, Shafran, et al., 2020). Käll et al.'s iCBT focuses on person-level psychological factors contributing to the maintenance of loneliness; it aims to help challenge maladaptive thoughts and encourage social behaviors (more information on Käll et al.'s iCBT available at [www.iterapi.se/sites/solus/](http://www.iterapi.se/sites/solus/)) (Käll, Shafran, et al., 2020). Following Käll et al.'s iCBT, the loneliness intervention includes content relating to understanding loneliness, setting goals and values, testing thoughts and behaviors, making plans, gaining social confidence, and overcoming barriers. Broadly, the intervention uses behavioral activation, cognitive restructuring, and behavioral experimentation strategies. The loneliness interventions also pull content from Jessica Schleider et al.'s single-session mental health interventions (<http://www.schleiderlab.org>) and take inspiration from their interventions' aesthetics and their strategy of using Qualtrics to develop and provide the intervention. Both the 30-minute SSI and 3-week intervention are text-based and self-guided.

The 3-week intervention includes three 10-20-minute self-guided sessions (participants complete the first session when they start the study, the next session a week later after they receive an email with it, and the final portion the next week when they receive another email).

In the control condition, participants complete a supportive therapy SSI, called "The Sharing Feelings Project", of roughly equivalent length and style to the loneliness SSI (J. L. Schleider & Weisz, 2019). The supportive therapy SSI, which researchers

borrowed from the Lab from Scalable Mental health, “encourages participants to express emotions to close others”, but “does not teach specific skills”. (J. L. Schleider et al., 2022; J. Schleider & Weisz, 2018). Previous work showed this control to be slightly less efficacious in improving mental health outcomes in adolescents than a growth mindset SSI and a behavioral activation SSI (J. L. Schleider et al., 2022; J. Schleider & Weisz, 2018). Researchers modified the supportive therapy SSI to make it relevant to both teens and adults, as it was originally designed for teens only (link to SSI: <https://osf.tvio/u4axs/>, license: <http://creativecommons.org/licenses/by-nc-sa/4.0/>) (J. L. Schleider & Weisz, 2019).

## **Hypotheses**

Researchers’ primary hypothesis is that participants randomized to the loneliness SSI will have greater reductions in self-reported loneliness between baseline and 8-week follow-up than those who are randomized to the active control SSI.

As secondary hypotheses, researchers predict greater improvements in distress (DASS-9), social anxiety, general self-efficacy, hopelessness, meaning and purpose in life, and adaptive actions and thoughts in the loneliness SSI condition relative to the control SSI. Researchers also hypothesize that participants who are randomized to the 3-week version of the loneliness intervention will report greater reductions in loneliness than those who are randomized to either the control condition or the 30-minute SSI.

### *Exploratory Hypotheses*

1. Having an insight experience during the intervention is associated with greater improvement in mental health outcomes between baseline and week 8.
2. Greater self-efficacy at baseline is associated with greater reduction in loneliness between baseline and week 8.
3. Greater engagement with the SSI platform predicts greater improvement in loneliness between baseline and week 8.

## **Analysis plan**

### *Main analysis*

The main DV is the change in loneliness (UCLA Loneliness Scale - 20 item Version 3) from baseline to 8-week follow-up. In the main analysis, researchers will test between-group differences across experimental conditions in change in loneliness from baseline to 8-week follow-up. Researchers will use a mixed-effects model predicting loneliness with condition, measurement time point, and the 2-way interaction between condition and time point as predictors and a participant identifier as a random intercept. Using the “lme4” package in R, these analyses will take the following form:

```
lmer(loneliness ~ time*condition + (1|study_id))
```

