#### *Additional analyses*

1. Researchers will duplicate the main analysis with the subset of participants who did not meet criteria for struggling with loneliness and thereby participated in the study without being compensated.
2. Researchers will duplicate the main analysis with the subset of participants who completed the week 8 follow-up.
3. Researchers will duplicate the main analysis but will include the following covariates in the mixed-effects model: gender (multiple choice), age (continuous), ethnicity (categorical), sexual orientation (categorical), education level (categorical), socioeconomic status (continuous), if participants completed the study on a computer, tablet, or phone, and whether participants answered at least one written-response question.
4. Researchers will use a one-way ANOVA to test between-group differences in loneliness at 8-week follow-up. If the omnibus ANOVA produces a significant F-score, researchers will conduct two planned contrasts to compare the experimental condition to each other condition, and will compute Cohen's ds of these comparisons. Researchers will run the same ANOVA on the 4-week follow-up data. Researchers will also conduct these ANOVAs on secondary outcomes and at post-intervention for outcomes collected then.
5. Researchers will calculate Cohen's d effect sizes reflecting within-group intervention effects on the loneliness for each condition from baseline to 4-week and 8-week follow-ups. They will also do so for each secondary DV

6. Researchers will run four logistic regression models with dropout as the outcome baseline measures as predictors to determine if they predict which participants drop out either before completing the intervention, before the post-intervention questions, or before the 4- and 8-week follow-ups.

*Additional analyses testing exploratory hypotheses*

1. To compare change in mental health outcomes across presence of an insight experience, researchers will conduct a mixed-effects model with loneliness as the outcome, timepoint, insight experience, and the interaction between the two as predictors, and a participant identifier nested within experimental condition as a random intercept.

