### *Main analysis*

The main analysis compares change in distress from baseline to 8-week follow-up across experimental conditions. Researchers will use a mixed-effects model predicting distress with condition, measurement time point (1 = baseline, 2 = 4-week follow-up, 3= 8-week follow-up), and the 2-way interaction between condition and measurement time point as IVs and a participant identifier as a random intercept. Using the “lme4” package in R, this analysis will take the following form:

```
lmer(distress ~ time*condition + (1|study_id))
```

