#### *Additional analyses*

1. Duplicate the main analysis with the subset of participants who did not meet criteria for struggling with distress and thereby participated in the study without being compensated.
2. Duplicate the main analysis comparing the change in distress from baseline to week 4 follow-up rather than to week 8.
3. Duplicate the main analysis with the subset of participants who completed the week 8 follow-up.
4. Duplicate the main analysis but with the following covariates included in the mixed-effects model: gender (multiple choice), age (continuous), ethnicity (categorical), sexual orientation (categorical), education level (categorical), socioeconomic status (continuous), and if participants completed the study on a computer, tablet, or phone.
5. Use a one-way ANOVA to test between-group differences in distress at 8-week follow-up. If the omnibus ANOVA produces a significant F-score, researchers will conduct two planned contrasts to compare the experimental condition to each other condition, and will

compute Cohen's ds of these comparisons. Researchers will run the same ANOVA on the 4-week follow-up data and at post-intervention for outcomes collected then. Researchers will also conduct these ANOVAs on secondary outcomes.

6. Calculate Cohen's d effect sizes reflecting within-group intervention effects on distress for each condition from baseline to 4-week and 8-week follow-ups.
7. Run four logistic regression models with dropout as the outcome baseline measures as predictors to determine if they predict which participants drop out either before completing the intervention, before the post-intervention questions, or before the 4- and 8-week follow-ups.
8. Duplicate the main analysis including data from suspected bots/scammers.

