#### *Additional analyses*

1. Duplicate the main analysis with the subset of participants who did not meet criteria for struggling with loneliness and thereby participated in the study without being compensated.

2. Duplicate the main analysis comparing the change in loneliness from baseline to week 4 follow-up rather than to week 8.
3. Duplicate the main analysis with the subset of participants who completed the week 8 follow-up.
4. Duplicate the main analysis but with the following covariates included in the mixed-effects model: gender (multiple choice), age (continuous), ethnicity (categorical), sexual orientation (categorical), education level (categorical), socioeconomic status (continuous), and if participants completed the study on a computer, tablet, or phone.
5. Use a one-way ANOVA to test between-group differences in loneliness at 8-week follow-up. If the omnibus ANOVA produces a significant F-score, researchers will conduct two planned contrasts to compare the experimental condition to each other condition, and will compute Cohen's ds of these comparisons. Researchers will run the same ANOVA on the 4-week follow-up data and at post-intervention for outcomes collected then. Researchers will also conduct these ANOVAs on secondary outcomes.
6. Calculate Cohen's d effect sizes reflecting within-group intervention effects on loneliness for each condition from baseline to 4-week and 8-week follow-ups.
7. Researchers will run four logistic regression models with dropout as the outcome baseline measures as predictors to determine if they predict which participants drop out either before completing the intervention, before the post-intervention questions, or before the 4- and 8-week follow-ups.
8. Duplicate the main analysis including data from suspected bots/scammers.

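### In all three studies the primary mixed model estimates a separate baseline mean per arm and the follow-up ANOVAs ignore baseline: a modest precision loss of unknown size, with a standard error that depends on the random-intercept structure

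*Combined protocol and SAP*

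**What the plan says.** The Main analysis sections of Study 1 (headed Aim 1) and Study 3 give "lmer(loneliness ~ time*condition + (1|study_id"; Study 2 gives "lmer(distress ~ time*condition + (1|study_id". The target is the between-arm difference in change from baseline to week 8. Studies 2 and 3 define "measurement time point (1 = baseline, 2 = 4-week follow-up, 3= 8-week follow-up" without saying whether time is a factor or numeric; Study 1 gives no coding.

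The Additional analyses then compare follow-up scores with no baseline term: "Researchers will use a one-way ANOVA to test between-group differences in loneliness at 8-week follow-up" (Study 1, item 4), "Use a one-way ANOVA to test between-group differences in distress at 8-week follow-up" (Study 2, item 5) and "Use a one-way ANOVA to test between-group differences in loneliness at 8-week follow-up" (Study 3, item 5), repeated at week 4 and for secondary outcomes. The week 4 repeats in item 2 of Studies 2 and 3 reuse the primary model, for example "Duplicate the main analysis comparing the change in distress from baseline to week 4 follow-up rather than to week 8".

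The covariate-adjusted repeats (Study 1 item 3; Studies 2 and 3 item 4) list demographics and device, plus a written-response indicator in Study 1, but not the baseline outcome score. That score can enter only through the Missing data handling rule, which adds a covariate when a baseline imbalance test finds an effect. Tables 1, 3 and 5 show that each repeated outcome is measured at baseline, except the count of resource views.

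**The concern.** Crossing time with condition brings in a condition main effect, so each arm gets its own baseline mean. According to the Inclusion criteria, participants are randomised after completing baseline, so expected baseline means are equal among those randomised. The primary model does not use that fact, and the follow-up ANOVAs do not use the baseline score at all.

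Precision is at stake for the primary contrast in three studies and for every secondary outcome with both a baseline and a follow-up score. Outcomes measured only after the intervention (program feedback, credibility and expectancy, insight, star rating) and resource views are unaffected.

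The same formula has a second consequence. A random intercept alone imposes one variance and one correlation across visits. If scores 8 weeks apart correlate less than scores 4 weeks apart, the model understates the variance of the baseline-to-week-8 change, and its p-values are too small.

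**Working it through.** The plan states no figure to reproduce. The available text gives no n, SD, correlation or retention, so all inputs below are assumptions: three equal arms, time as a factor, r = baseline-to-week-8 correlation, k = baseline SD divided by follow-up SD. Steps 1 to 3 assume equal correlation between visits.

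**1. Gain from a common baseline, complete data.** In units of 2 x (follow-up variance)/n per arm:
- separate baseline means: k² + 1 − 2rk
- common baseline mean, unstructured covariance: 1 − r²
- proportional cut: (k − r)² / (k² + 1 − 2rk), which is (1 − r)/2 when k = 1.

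For k = 1, r = 0.5: 0.25/1.00 = 25%. For k = 1, r = 0.8: 0.04/0.40 = 10%. For k = 0.8, r = 0.5: 0.09/0.84 = 10.7%. For k = 0.8, r = 0.8: 0/0.36 = 0%.

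**2. With dropout.** Generalised least squares, monotone dropout, unstructured covariance in both models. Cut in variance of the week 8 contrast at r = 0.5, 0.6, 0.7, 0.8:

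| Retention week 4/week 8 | k = 1 | k = 0.9 | k = 0.8 |
|---|---|---|---|
| complete | 25, 20, 15, 10% | 17.6, 12.3, 7.3, 2.7% | 10.7, 5.9, 1.9, 0.0% |
| 80%/70% | 19.1, 15.1, 11.2, 7.4% | 13.2, 9.1, 5.3, 2.0% | 7.8, 4.3, 1.4, 0.0% |
| 60%/50% | 14.5, 11.3, 8.3, 5.4% | 9.8, 6.7, 3.9, 1.4% | 5.8, 3.1, 1.0, 0.0% |

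A k below 1 is plausible because the main analyses keep only people above a baseline screen, which compresses the baseline spread. In power terms (assumed effect 0.3 SD, 100 randomised per arm, r = 0.6, two-sided 0.05), power rises from 0.66 to 0.76 with complete data and k = 1, and from 0.46 to 0.48 at 60%/50% retention and k = 0.8.

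**3. Why the covariance must change too.** If a common baseline is imposed but the random intercept is kept, complete data at k = 0.8 give variance changes of −9.4, −3.5, +2.3 and +8.0% at r = 0.5 to 0.8. Precision can then be lost.

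**4. Standard error of the planned model when correlation decays.** With complete data and equal SDs, the random-intercept fit works with the average correlation across visit pairs.
- Mild decay (0.8 adjacent, 0.7 over 8 weeks): average (0.8 + 0.8 + 0.7)/3 = 0.767. Model variance 2(1 − 0.767) = 0.467; true variance 2(1 − 0.7) = 0.600. The 1.96 cut-off acts as 1.96 x √(0.467/0.600) = 1.73, so type I error is about 8%.
- AR-type decay (adjacent √0.7 = 0.837): average 0.791. Model variance 0.418 against 0.600. The cut-off acts as 1.64, so type I error is about 10%.

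The common-baseline unstructured model has true variance 1 − 0.49 = 0.51, which is 15% below 0.600. Its reported SE is nevertheless larger than the planned model's: √(0.51/0.467) = 1.05 times and √(0.51/0.418) = 1.10 times.

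**5. Follow-up ANOVAs.** ANCOVA on baseline cuts variance by about r²: 25, 36, 49, 64% at r = 0.5 to 0.8. As an illustration of the screen (screen-to-baseline correlation 0.8, top half kept), r falls to 0.41 to 0.72 and the cut to about 17 to 52%.

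**6. The imbalance rule is not a repair.** It is triggered by a test rather than prespecified. With complete data, a participant-level covariate entered as a main effect leaves the time-by-condition estimate and its SE unchanged. Baseline would also stand in the model as both outcome and predictor.

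**The case against.** The strongest reply is that the planned model is an accepted estimator which already uses baseline through change, and that the benefit may be close to nil: with high r, compressed baseline SD and heavy dropout the cut is 0 to 3%. That stands, and it is why the gain is called modest and unknown.

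The second reply is robustness. The Inclusion criteria remove people using information gathered after randomisation: self-declared non-serious participation, and suspicion factors such as survey duration and similar feedback answers. Some of these could differ by arm, so equal baseline means are guaranteed in the randomised set but only assumed in the analysed set. That stands too, and is why the planned model should still be reported.

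The third is timing. The update of February 20, 2023 in Study 1's Inclusion criteria shows that responses had already been inspected. Replacing Study 1's primary model after that is not free.

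The ANOVA gains are larger, but those are additional analyses, so the figures should not be carried over to the primary contrast.

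A reader might infer that separate baseline means make the primary comparison biased. They do not: that contrast still targets the difference in change. A reader might equally infer that the planned test is valid without condition and only precision is at stake. The documents do not support that either, because the stated model fixes a covariance structure that nothing in the text justifies.

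**Conclusion.** The point holds as an efficiency improvement with a condition on the standard error; it is not a demonstrated error in the plan. The precision gain for the primary contrast runs from 25% of variance down to about zero under the assumed r, SD ratio and retention, and nothing in the available text places the trials within that range. It comes from the common baseline mean. The unstructured covariance mainly protects the standard error and prevents a loss of precision when SDs differ, so the reported SE may rise even as true precision improves. The type I error figures of about 8% and 10% rest on assumed decay with complete data and equal SDs; they show sensitivity and are not estimates for these trials. The change is worth making because it is cheap and uses data already collected. The clearest case is ANCOVA in place of the follow-up ANOVAs.

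**What to change.** For each outcome with a baseline score:

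- Treat time as a factor. With numeric coding 1, 2, 3, dropping the condition term would equate the arms at time 0, not at baseline.
- Prespecify the week 8 contrast against the comparator named in each primary hypothesis: loneliness SSI against control SSI (Study 1), Blu Surfer against ABC Project (Study 2), Lonely Blu Surfer against Sharing Feelings (Study 3).
- Estimate it with one common baseline mean (condition only in the post-baseline time-by-condition terms) and unstructured covariance across visits, for example by generalised least squares with visit-specific variances. Take the week 4 contrast from the same fit. Include the post-intervention visit for self-efficacy and hopelessness. Participants with baseline only stay in, as Missing data handling intends.
- Replace the follow-up ANOVAs with ANCOVA on the same measure's baseline.
- Do not enter baseline as both an outcome row and a covariate, including through the imbalance rule.
- Report the planned model alongside, because of the post-randomisation exclusions.

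For Study 1, date and document the change and make it before any outcome comparison by arm. If that is no longer possible, keep the planned model as primary and report the new one as a sensitivity analysis.

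Cost: a little more model code, SAP wording, one extra analysis per outcome and, for Study 1, a documented late change. No new data are needed.

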### *Secondary analysis*

Researchers will re-run the main analysis separately for each secondary DV, although the “time” variable will compare across different timepoints depending on the DV (see table 1).

